10.6 Investigational Medicinal Product

10.6.1 Identity

[REDACTED]

[REDACTED]

[REDACTED]

[REDACTED]

A large black rectangular redaction box covers the majority of the page content. There are a few small white rectangular areas, likely representing redacted lines of text, located near the top right, bottom right, and bottom center of the redacted area.

10.6.2 Receipt and Storage

The Sponsor must notify the Principal Investigator, or the Project Manager, prior to dispatch of IMP supplies, and of the anticipated date of their arrival. IMP should arrive at the study site at least 7 days before the first dosing day. The Sponsor shall address all supplies to:

The Production Manager

The Pharmacy

Simbec-Orion Clinical Pharmacology Unit
[name]
[name], UK

[figure not shown]
Upon receipt, supplies will be dealt with as per Simbec-Orion SOP SR-IMP 053. Temperature monitors included with shipments will be downloaded. The Sponsor will confirm that the transportation conditions are acceptable.

The IMPs will be stored securely under quarantine in a segregated, study-specific location, at <-70°C. The shipping documentation and bulk product Qualified Person (QP) certification will be reviewed. The supplies will subsequently be removed from quarantine and approved for use.

10.6.3 Assembly and Release

The IMP will be assembled into unit doses by suitably trained Simbec-Orion staff according to the Simbec-Orion SOP SR-IMP 015.

The IMP will be labelled as specified in Annex 13 (manufacture of IMPs) of the European Commission guide to Good Manufacturing Practice (GMP)^[13].

10.6.4 Administration

10.6.4.1 Placebo Training

Each participant will be administered with 150 mL of sodium bicarbonate solution 2% weight/volume (w/v) at the Screening Visit, in order to practice oral administration prior to enrolment on the study.

10.6.4.2 Treatment Period

The following IMPs will be administered:

Cohort 1 (n=9)	3 doses of 1×10^9 CFU of ZH9PA (6 participants) Placebo (3 participants)
Safety Review Meeting (up to Day 7 safety data)	
Cohort 2 (n=18)	3 doses of 1×10^{10} CFU of ZH9PA (12 participants) Placebo (6 participants)
Safety Review Meeting (up to Day 7 safety data)	
Cohort 3 (n=18)	3 doses of 1×10^{10} CFU of ZH9PA and 1×10^{10} CFU of ZH9 (12 participants) Placebo (6 participants)

The IMPs will be administered following 90 mins of fasting (water is permitted).

A dose leader design will be implemented with 2 participants being dosed on the first dosing day of EACH cohort. Of these 2 participants, 1 will be randomised to receive active drug and 1 randomised to receive placebo. The remainder of the cohort will be randomised and dosed at least 24 h later pending an acceptable safety profile in the dose-leader group and will contain at least 1 additional placebo participant. The decision to proceed will be confirmed by the Investigator or delegate and communicated with the Sponsor. This design allows maintenance of the “blind”.

IMP administration will be documented in the eCRF.

There will be 21 days between doses.

10.6.5 Return/Destruction

All used IMP containers and unused IMP (with the exception of any prepared solution that is not used for dosing) will be held under quarantine pending return/destruction.

The Sponsor must provide approval for return/destruction of all remaining IMP within 8 weeks of study completion.

All returns will be arranged at the earliest available delivery date.

For IMP destruction, the Sponsor will receive the Certificate of Destruction 4 to 6 weeks from the date of removal from site.

10.6.6 Method of Assigning Participants to Treatment Groups

Participants will be allocated to treatment groups according to a randomisation code produced by Simbec-Orion using the PROC PLAN procedure of Statistical Analysis Software (SAS®) (version 9.3 or higher). The randomisation code will include 2 dose-leaders (1 active:1 placebo) in each cohort.

Participants will be numbered sequentially from 001 (i.e. 001, 002 etc.). Replacement participants will be assigned the same randomisation as the participant they are replacing, however, 100 will be added to the number (i.e. 101 would replace 001 etc.).

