10.5.5 Removal of Participants from Therapy or Assessment

Each participant will be informed of his/her right to withdraw from the study at any time and for any reason.

An Investigator will withdraw a participant from the study at any time for any of the following reasons:

- If a participant experiences a serious or intolerable AE, that prevents him/her from continuing participation in the study.
- If a participant incurs a significant protocol violation which impacts on his/her safety or the scientific integrity of the study (this will be discussed on a case-by-case basis with the Sponsor).
- At the request of the Sponsor.
- If it is considered that the participant's health is compromised by remaining in the study or the participant is not sufficiently cooperative.
- If a participant is lost to follow-up.

Participants who meet one or more of the following stopping criteria will receive no further doses of the study vaccine but will be followed up for safety:

- Severe systemic reaction, e.g., anaphylaxis.
- Persistent febrile reaction ($\geq 38.5^{\circ}\text{C}$ for ≥ 12 hours) at the Investigator's discretion
- SAE related to the study agent (serious adverse reaction (SAR) or suspected unexpected serious adverse reaction (SUSAR))

The medical safety of the participant is of paramount importance when discussing study continuation.

The reasons for any participant withdrawal will be recorded on the study completion form of the electronic case report form (eCRF).

If a participant is withdrawn or chooses to withdraw from the study for any reason every possible effort will be made to perform the evaluations described for the post-study follow-up (see [Table 10.7.1](#)). The data collected from withdrawn participants will be included in the study report.

In the event of any abnormalities considered to be clinically significant, participants will be followed up with appropriate medical management until values are considered to be clinically acceptable. Referral or collaborative care will be organised if considered necessary.

A total of 45 participants are required to complete the study. Participants who withdraw from the study before receiving any IMP will be replaced. Participants who are withdrawn from the study due to significant drug-related AEs will not be replaced. Replacement of all other participants withdrawn from the study after receiving IMP will be decided on a case-by-case basis by the Principal Investigator (or deputy) and Sponsor.

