10.6.9 Blinding

A designated individual from the IMP Management Department at Simbec-Orion will generate the randomisation code under the guidance of a statistician. An independent unblinded dosing team will be assigned at the site to supervise administration of the IMP or placebo. This dosing team will have no other involvement in the study. All other site and Sponsor personnel involved in the study will be blinded with regard to the IMP being administered. The Pharmacist (or designee) responsible for the preparation of participant doses and emergency code break envelopes will not be blinded and a copy of the original randomisation code will be issued to the pharmacist (or designee) for this purpose.

Participant doses: Once the randomisation code has been authorised as per Simbec-Orion SOPs, each participant dose will be packaged and labelled for individual participants by designated individuals from the IMP Management Department at Simbec-Orion on behalf of the Sponsor.

Code break envelopes: Once the randomisation code has been authorised as per Simbec-Orion SOPs, the Pharmacist (or designee) will produce individual sealed code-break envelopes that contain the treatment allocation(s) for each participant. The envelopes will be stored in the restricted access pharmacy. A set of code break envelopes will also be provided to the person responsible for PV.

Emergency unblinding: Where the site requires emergency access to an individual participant code Simbec-Orion will break the blind via the code break envelopes stored in the pharmacy without prior consultation with the Sponsor. In such an event, the Sponsor's Responsible Physician will be notified as soon as possible via email. Please refer to Simbec-Orion SOP SR-CPU 041.

Non-emergency unblinding: If an Investigator believes that knowledge of the IMPs received by a participant is essential for appropriate treatment of an AE, the code will be broken via the code break envelopes stored in the pharmacy. Where practical, the Investigator should ideally

consult the Sponsor before breaking the code. In any event, the Sponsor will be informed as soon as practical whenever the code has been broken for a participant.

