If the blind needs to be broken for an individual participant, the date and reason will be recorded in the participant's eCRF. The Investigator will not reveal the unblinded treatment code to any other member of the clinical team involved in the study or to the Study Monitor. If the code is broken for any individual participant, the participant will be withdrawn from the study and the procedures accompanying withdrawal performed. If the code is broken without justification, this will be deemed a serious protocol deviation.

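### A participant whose code has been broken may be replaced like for like, so an Investigator who saw the code would know the replacement's arm

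*Combined protocol and SAP*

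**What the plan says.** Three sections of the protocol bear on this.

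- **Section 10.6.6, allocation of replacements.** "Replacement participants will be assigned the same randomisation as the participant they are replacing, however, 100 will be added to the number". The example given is that "101 would replace 001 etc".
- **Section 10.6.9, code breaks.** In a non-emergency the trigger is an Investigator's own view: where "knowledge of the IMPs received by a participant is essential for appropriate treatment of an AE, the code will be broken". There is also an emergency route. The consequence is general: "If the code is broken for any individual participant, the participant will be withdrawn from the study and the procedures accompanying withdrawal performed". Onward disclosure is limited: "The Investigator will not reveal the unblinded treatment code to any other member of the clinical team involved in the study", nor may it go to the Study Monitor.
- **Section 10.5.5, who is replaced.** Withdrawals before any dose are replaced. "Participants who are withdrawn from the study due to significant drug-related AEs will not be replaced". For the rest, "Replacement of all other participants withdrawn from the study after receiving IMP will be decided on a case-by-case basis by the Principal Investigator"; a deputy may act instead, and the Sponsor shares the decision. The same section asks for 45 completers.

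Eligibility is assessed by an Investigator (Section 10.7.1.2), as are AE severity and relationship to IMP (Section 10.7.1.3.1). Section 10.6.9 says that site and Sponsor staff other than the dosing team and pharmacy are blinded.

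**The concern.** Each rule is reasonable alone. Like-for-like replacement keeps the 6:3 and 12:6 splits and the 1:1 dose-leader pairs. The difficulty comes when the rules are followed in sequence. An opened code belongs to a slot on the randomisation list, and a replacement is put into that same slot. The code is therefore already open when the new participant arrives.

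At stake is allocation concealment and observer blinding for that one replacement. The person who knows the arm may take part in the decision to replace, may confirm eligibility, and may grade AEs and judge their relatedness. Those judgements feed part of the primary endpoint (Section 10.9.1.1), the TEAE summaries by severity and relationship (Section 10.9.1.3.3) and the dose-escalation stopping criteria (Section 10.2.2.2).

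**Working it through.** **Step 1. The design figures.** Cohorts: 9 + 18 + 18 = 45. Active: 6 + 12 + 12 = 30. Placebo: 3 + 6 + 6 = 15. These agree with Section 10.1. Section 10.9.2 gives no formal sample-size calculation, so there is no power figure to reproduce.

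**Step 2. The chain of rules.**

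| Event | Rule | Does it stop the chain? |
|---|---|---|
| Code opened for an AE | 10.6.9 | No. An Investigator now knows the arm |
| Participant withdrawn | 10.6.9 | No. A slot opens |
| Replacement considered | 10.5.5 | Only if the withdrawal is for a significant drug-related AE, or the decision-makers decline |
| Replacement allocated | 10.6.6 | No. Same allocation, with no exception for an opened code |
| Replacement enrolled and assessed | 10.7.1.2, 10.7.1.3.1 | No. Any Investigator may do it; the one who saw the code is not excluded |

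The disclosure limit in 10.6.9 keeps the code from spreading. It does not restrict what the Investigator who holds it may do next.

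**Step 3. How predictable the arm is.** Each cohort has one active and one placebo dose leader (Section 10.6.6), so the blinded probability of active is:

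- dose leader: 1/2 = 50%
- non-leader, Cohort 1: (6 − 1)/(9 − 2) = 5/7 = 71.4%
- non-leader, Cohorts 2 and 3: (12 − 1)/(18 − 2) = 11/16 = 68.8%
- ignoring leader status: 6/9 = 12/18 = 66.7%

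For a replacement who inherits an opened code, the arm is known with probability 100% to whoever saw it. With a fresh draw from a concealed list at the cohort's 2:1 ratio, the best guess would be about 2/3 = 67%.

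**Step 4. Weight of one such replacement.** As a share of the planned arm: 1/3 of placebo or 1/6 of active in Cohort 1; 1/6 of placebo or 1/12 of active in Cohorts 2 and 3. The withdrawn participant was dosed and so stays in the Safety Set (Section 10.9.1.2), which makes that arm one larger. The shares there are 1/4 or 1/7 in Cohort 1, and 1/7 or 1/13 in Cohorts 2 and 3. These are shares of an arm, not estimates of bias.

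**Step 5. Direction.** The bar on replacement turns on drug-relatedness. If the opened code shows placebo, the AE is less likely to be called drug-related, so the slot is more likely to stay replaceable and the replacement would be known to be on placebo. This is an inference about judgement, not something the protocol states.

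**The case against.** The strongest reply is that the path is narrow. It needs a code break, a withdrawal not due to a significant drug-related AE, a discretionary decision to replace, and a code-holder who goes on to handle the replacement. The decision is shared with the Sponsor, who under 10.6.9 is told that a code was broken, not what it showed. The Principal Investigator has a deputy, and nothing requires the code-holder to be the assessor. All of this stands and limits the reach. It does not close the gap, because following the protocol as written still permits the sequence.

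A reader might infer more than the documents support:

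- *That the linked number unblinds replacements.* To anyone who has not seen the code, 101 reveals only that 001 was replaced. An unlinked number would not help the code-holder forget whose slot is being filled.
- *That the site team is unblinded.* Section 10.6.9 forbids passing the code to the clinical team or the Study Monitor.
- *That the arm is known before the replacement consents.* Section 10.9.2 foresees screening enough people at the start, so the replacement may already have consented.
- *That the primary endpoint rests on Investigator grading.* It also covers laboratory tests, vital signs and physical examination, and the planned Fisher's exact test compares TEAE incidence.
- *That every replacement should come from a 2:1 reserve list.* That could break a 1:1 dose-leader pair replaced before dosing. It could also disturb the footnote to Section 10.2, where 14 − 6 = 8 active participants assumes six on placebo.

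**Conclusion.** The point holds in a limited form. Nothing in Sections 10.5.5, 10.6.6 or 10.6.9 exempts a participant whose code was broken from like-for-like replacement. Where such a participant is replaced, the arm is certain to any Investigator who saw the code, instead of a best guess of 50% (dose leader) or 69% to 71% (others), and that Investigator may decide on, enrol or assess the replacement.

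The number affected is unknown. A range of 0 to 2 is an assumption made here. No effect on any trial result can be estimated from the documents. The conclusion rests on reading the Section 10.6.6 rule as applying to all replacements, as its wording does.

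One related matter is not counted here. Section 10.3 provides for unblinding the Investigators and the Monitor to participants with a *Salmonella*-positive Day 70 stool, while Section 10.6.9 withdraws anyone whose code is broken and bars disclosure to the Monitor. Those passages need reconciling. Read literally together, they would be a second route to the same problem.

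**What to change.** Amend Section 10.6.6 as follows:

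1. Keep like-for-like replacement for participants whose code is still sealed. This preserves 6:3, 12:6 and the 1:1 dose-leader pairs.
2. State that a participant whose code has been broken is either not replaced, or is replaced from a short reserve list generated with the main randomisation code and held by the unblinded pharmacist, concealed from all blinded staff. Section 10.6.9 already gives the pharmacist a copy of the code, so no new role is needed.
3. Add a cross-reference in Section 10.5.5, so that the case-by-case decision is made with this rule in view.

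The cost is about one sentence of protocol text and, if the reserve list is chosen, a few extra lines on the randomisation list. Not replacing loses one completer each time (44 instead of 45 for a single case). Using the reserve list can move a cohort's split by one for each such replacement. If that happens in Cohort 2 before the Cohort 3 decision, the pharmacist should recheck the minimum of 8 active participants. Changing the numbering alone would not solve the problem.

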10.6.7 Selection of Doses in the Study

ZH9 is a live attenuated, oral vaccine, against typhoid fever. It was previously identified as MICRO-TY. ZH9 and consists of the vaccine strain, S. Typhi (Ty2 aroC⁻ ssaV⁻) ZH9.

Individual participant treatments will be dispensed by the pharmacist or designee and labelled in accordance with Annex 13 of “The Rules Governing Medical Products in European Community, volume 4 Good Manufacturing Practice for Medicinal Products”^[4].

The following dosing strategy will be employed:

Cohort	Dose schedule	Dose level
1	Day 0, 21, 42	1x10 ⁹ CFU ZH9PA or placebo
2	Day 0, 21, 42	1x10 ¹⁰ CFU ZH9PA or placebo
3	Day 0, 21, 42	1x10 ¹⁰ CFU ZH9PA and 1x10 ¹⁰ CFU ZH9 or placebo

The dose levels chosen are based on the previous clinical experience with ZH9. These studies have determined that a dose of 1×10^{10} CFU is well tolerated and induces immune responses to LPS 0:9. ZH9PA is derived from ZH9, being modified to carry heterologous antigens. Other potential products, derived from ZH9, have been used to deliver heterologous antigens in clinical trials i.e. ETEC LT antigen and Hepatitis B core antigen, at doses of 1×10^9 CFU and 1×10^{10} CFU respectively. Based on these data it is considered appropriate that the starting dose for ZH9PA is 1×10^9 CFU. To date, ZH9 has been administered at a maximum dose of 1.7×10^{10} CFU with no significant adverse effects; therefore, administering a maximum bacterial load of 2×10^{10} CFU, of ZH9PA with ZH9 is considered appropriate.

10.6.8 Timing of Dose for Each Participant

Two (2) dose leaders (1 active:1 placebo) will be dosed first in each cohort. The remainder of the cohort will be dosed at least 24 h later pending an acceptable safety profile in the dose-leader group. A telephone call will be made to the dose leaders on the morning of Day 1 to assess the safety profile.

10.6.9 Blinding

A designated individual from the IMP Management Department at Simbec-Orion will generate the randomisation code under the guidance of a statistician. An independent unblinded dosing team will be assigned at the site to supervise administration of the IMP or placebo. This dosing team will have no other involvement in the study. All other site and Sponsor personnel involved in the study will be blinded with regard to the IMP being administered. The Pharmacist (or designee) responsible for the preparation of participant doses and emergency code break envelopes will not be blinded and a copy of the original randomisation code will be issued to the pharmacist (or designee) for this purpose.

Participant doses: Once the randomisation code has been authorised as per Simbec-Orion SOPs, each participant dose will be packaged and labelled for individual participants by designated individuals from the IMP Management Department at Simbec-Orion on behalf of the Sponsor.

Code break envelopes: Once the randomisation code has been authorised as per Simbec-Orion SOPs, the Pharmacist (or designee) will produce individual sealed code-break envelopes that contain the treatment allocation(s) for each participant. The envelopes will be stored in the restricted access pharmacy. A set of code break envelopes will also be provided to the person responsible for PV.

Emergency unblinding: Where the site requires emergency access to an individual participant code Simbec-Orion will break the blind via the code break envelopes stored in the pharmacy without prior consultation with the Sponsor. In such an event, the Sponsor's Responsible Physician will be notified as soon as possible via email. Please refer to Simbec-Orion SOP SR-CPU 041.

Non-emergency unblinding: If an Investigator believes that knowledge of the IMPs received by a participant is essential for appropriate treatment of an AE, the code will be broken via the code break envelopes stored in the pharmacy. Where practical, the Investigator should ideally

consult the Sponsor before breaking the code. In any event, the Sponsor will be informed as soon as practical whenever the code has been broken for a participant.

If the blind needs to be broken for an individual participant, the date and reason will be recorded in the participant's eCRF. The Investigator will not reveal the unblinded treatment code to any other member of the clinical team involved in the study or to the Study Monitor. If the code is broken for any individual participant, the participant will be withdrawn from the study and the procedures accompanying withdrawal performed. If the code is broken without justification, this will be deemed a serious protocol deviation.

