METHODOLOGY: This is a Phase I, randomised, double-blind, placebo-controlled, parallel group, single-centre study involving 45 healthy participants. The aim is to evaluate a combination vaccine against enteric fever comprising the live attenuated Salmonella strain ZH9 (previously tested in a number of clinical trials as a typhoid vaccine) and its modified derivative, ZH9PA, in which the typhoid antigens LPS O:9 and Flagellin H:d have been substituted by the Paratyphi A antigens, LPS O:2 and Flagellin H:a. ZH9PA has not previously been tested in humans; therefore, the first two cohorts comprise a dose escalation of this component alone, followed by a final cohort in which the combination is tested at a single dose level. The study will remain fully blinded until Day 70, when a stool sample is taken to assess if participants are shedding the bacterial strains of the vaccine in their faeces. The Investigators and the Monitor may be unblinded to the treatment allocation of participants who have a stool culture positive for any Salmonella strain, as it will be presumed to be one of the vaccine strains, and the participant will receive a course of antibiotics.
NUMBER OF PARTICIPANTS: 45 healthy participants 18 to 45 years of age, inclusive.

INCLUSION CRITERIA:**To be confirmed at Screening**

1. Healthy male and female participants 18 to 45 years of age, inclusive.
2. Female participant of childbearing potential willing to use 2 effective methods of contraception, i.e., established method of contraception + condom, if applicable (unless of non-childbearing potential or where abstaining from sexual intercourse is in line with the preferred and usual lifestyle of the participant) from the first dose until 2 months after the last dose of IMP.
3. Female participant of non-childbearing potential. *For the purposes of this study, this is defined as the participant being amenorrhoeic for at least 12 consecutive months or at least 4 months post-surgical sterilisation (including bilateral fallopian tube ligation or bilateral oophorectomy with or without hysterectomy).*
4. Female participant of childbearing potential or non-childbearing potential with a negative pregnancy test at Screening.

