Participants will be admitted to the Clinical Unit on the morning of Day 21, with assessments performed as per [Table 10.7.1](#). Following a 90-min fast prior to dose administration, participants will receive the second dose, and then continue to fast for a further 90 mins post dose administration; water will be allowed. Following the completion of the 4h post-dose assessments and at the discretion of the Investigator, the participants will be discharged from the Clinical Unit. Participants will return to the Clinical Unit on Day 24 for safety assessments as per [Table 10.7.1](#). For the 7 days following the second dosing visit (Day 22 to Day 28) participants will be required to record their body temperature at home twice a day, i.e. once in the morning and once in the evening (a thermometer and a diary will be provided to record body temperature). Participants will return to the Clinical Unit on Day 28 with the diary and to give a blood sample for the PBMC/ALS assay; assessments will be performed as per [Table 10.7.1](#).

Participants will be admitted to the Clinical Unit on the morning of Day 42, with assessments performed as per [Table 10.7.1](#). Following a 90-min fast prior to dose administration participants will receive the third dose, and then continue to fast for a further 90 mins post dose administration; water will be allowed. Participants will return on Day 45 for safety assessments as per [Table 10.7.1](#). For the 7 days following the third dosing visit (Day 43 to Day 49) participants will be required to record their body temperature at home twice a day, i.e. once in the morning and once in the evening (a thermometer and a diary will be provided to record body temperature). Participants will return to the Clinical Unit on Day 49 with the diary and to give a blood sample for the PBMC/ALS assay; assessments will be performed as per [Table 10.7.1](#).

Participants will return to the Clinical Unit on Day 70 to provide a stool sample for bacteriology. If the stool sample is positive for any *Salmonella* strain at Day 70, it will be presumed to be one of the vaccine strains, and participants will be asked to return to the Clinical Unit to receive a course of antibiotic therapy. Participants who receive a course of antibiotics will be required to provide a repeat stool sample for bacteriology testing on Day 84, to confirm that shedding of the vaccine strains has ceased, as per [Table 10.7.1](#).

Post-Study Follow-Up (Day 85 to Day 224)

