10.3 Discussion of Study Design, including the Choice of Control Groups

This is a Phase I, first in human, randomised, double-blind, placebo-controlled, parallel group, study. Randomised, double-blind studies are the gold standard methodology to assess the safety, tolerability and efficacy of products and therefore, this design has been used for this study. In the case of this study, it will remain fully blinded until Day 70, when a stool sample is taken to assess if participants are shedding the bacterial strains of the vaccine in their faeces. The Investigators and the Monitor will be unblinded to the treatment allocation of participants who have a positive result for *Salmonella* and the participant will receive a course of antibiotics.

No benefit to participants is expected, as efficacy has not been evaluated for the ZH9/ZH9PA combination or for ZH9PA on its own; therefore, use of placebo as the control is considered acceptable in the healthy participants participating in the study. The use of the placebo control allows an assessment of the immune response and provides a background incidence of adverse events.

Previous work with ZH9 has shown that the double mutation does appropriately attenuate the bacteria, however it is known that the bacterial strains that make up the vaccine can be shed in the stools of participants. The vaccine strains are genetically modified organisms, and as such it is necessary to reduce environmental exposure and stool cultures are taken to ensure that participants are not shedding.

There remains a theoretical risk of the vaccine strains causing a systemic infection and so body temperatures will be taken for 7 days post each dose of vaccine. The vaccine strains are

sensitive to several antibiotics, which can be used to treat an infection in the unlikely event such an event occurs.

Three doses are to be studied, as vaccines usually require more than one dose to induce a robust immune response.

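### The section 10.6.9 rule withdrawing anyone whose code is broken has no exception for the planned Day 70 unblinding of stool-positive participants, whom section 10.1 expects back at Day 84

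*Combined protocol and SAP*

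**What the plan says.** Four places in the protocol bear on a participant whose Day 70 stool culture grows Salmonella.

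- **Section 10.6.9 (Blinding).** "If the code is broken for any individual participant, the participant will be withdrawn from the study and the procedures accompanying withdrawal performed". The sentence has no exception. The same paragraph forbids the Investigator to reveal the code to "any other member of the clinical team involved in the study or to the Study Monitor".
- **Section 10.3 (Discussion of Study Design).** "The Investigators and the Monitor will be unblinded to the treatment allocation of participants who have a positive result for" Salmonella. Here the unblinding is definite and includes the Monitor.
- **Synopsis, Methodology.** "The Investigators and the Monitor may be unblinded to the treatment allocation of participants" with a positive culture. Here the same step is optional.
- **Section 10.1 (Overall Study Design and Plan).** "Participants who receive a course of antibiotics will be required to provide a repeat stool sample for bacteriology testing on Day 84". Footnote 10 of Table 10.7.1 repeats this. Both assume that the participant is still in the study.

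Section 10.5.5 says what is sought from a participant who has been withdrawn: the evaluations of the post-study follow-up. Section 10.1 and Table 10.7.1 define these as telephone calls on Days 154 and 224.

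**The concern.** Site staff who receive a positive Day 70 culture have incompatible instructions. If they unblind as section 10.3 directs, 10.6.9 tells them to withdraw the participant, while 10.1 tells them to see that participant at Day 84. They must also share the allocation with the Monitor under one section and withhold it under another.

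The statistical stake is selective loss. The protocol presumes that any Salmonella found is a vaccine strain, so withdrawals triggered this way would fall almost entirely on the active arms. They would come two weeks before the visit that supplies the only serum antibody measurement after the full three-dose course and that closes the primary safety window. Missingness tied to a post-vaccination biological event in one arm cannot be assumed ignorable, and the missed Day 84 sample cannot be recovered later.

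**Working it through.** **1. Is Day 84 the only serum sample after dose 3?** Table 10.7.2 gives eight biochemistry draws of 3.5 mL, eight haematology draws of 3.0 mL, four PBMC/ALS draws of 64 mL and four serum Ig draws of 20 mL.

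8 × 3.5 + 8 × 3.0 + 4 × 64 + 4 × 20 = 28 + 24 + 256 + 80 = 388 mL

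This matches the stated total, so the schedule reads as intended. Serum Ig is drawn on Days 0, 21, 42 and 84. The Day 21 and Day 42 samples are taken before that day's dose (section 9.2), and dose 3 is given on Day 42. Only Day 84 follows dose 3, so a participant withdrawn at about Day 70 contributes 0 of 1.

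**2. What else falls at Day 84?** Laboratory tests, vital signs and physical examination, all components of the primary endpoint (section 10.9.1.1), and the repeat stool.

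**3. Timing.** Day 70 is 70 − 42 = 28 days after dose 3. Day 84 is 14 days later. With visit windows of ±1 and ±7 days, the gap runs from 77 − 71 = 6 to 91 − 69 = 22 days.

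**4. Does the withdrawal procedure recover Day 84?** No. Section 10.5.5 seeks only the follow-up calls. Those review adverse events that led to a healthcare visit, so they do not replace the Day 84 examination or sample.

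**5. Does 10.6.9 cover the Day 70 step elsewhere?** It describes two routes: emergency access, and knowledge essential for treating an adverse event. The planned Day 70 unblinding is described under neither and exempted from neither.

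**6. How many participants?** Active participants: 6 + 12 + 12 = 30. The documents give no shedding rate, so *p* below is an assumption. The second column is 30*p*; the third is 1 − (1 − *p*)^12.

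| Assumed Day 70 shedding | Expected removals of 30 | Chance of at least one in a 12-person active arm |
|---|---|---|
| 0% | 0 | 0% |
| 5% | 1.5 | 46% |
| 10% | 3 | 72% |
| 25% | 7.5 | 97% |
| 30% | 9 | 99% |

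**7. Effect on Day 84 results.** If a fraction *f* of an arm is dropped and its titres are *k*-fold higher than the rest, the remaining geometric mean titre (GMT) divided by the full-arm GMT is *k*^(−*f*). Both *k* and *f* are assumptions.

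- *k* = 2, *f* = 0.05: 2^(−0.05) = 0.966, about 3% lower.
- *k* = 2, *f* = 0.25: 2^(−0.25) = 0.841, about 16% lower.
- *k* = 1: no shift at any *f*.

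Precision falls even with no shift. The 95% CI half-width on the mean log titre is proportional to t(0.975, n − 1)/√n. At the same SD, losing 1 of 12 widens it by about 6%, and losing 3 of 12 by about 21%.

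**The case against.** The strongest reply is that nobody intends to drop these participants. The withdrawal sentence in 10.6.9 follows directly on the emergency and adverse-event code breaks, and the Day 70 unblinding is a separate planned step. Unblinding is not among the withdrawal reasons in section 10.5.5, and section 10.1 with footnote 10 schedules these people for Day 84. This stands as evidence of intent. It does not remove the conflict, because the 10.6.9 sentence covers any individual participant and is the only text that states the consequence of a broken code.

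A reader might infer several stronger points that the documents do not support:

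- **That the plan removes shedders.** This is one literal reading, contradicted by section 10.1.
- **That the Day 85-224 safety endpoint is lost.** Section 10.5.5 asks for every effort to obtain the Day 154 and 224 calls.
- **That post-dose-3 immunogenicity is lost altogether.** The Day 49 ALS sample precedes Day 70. Data already collected stay in the report, in the Safety Set and, with any post-baseline antibody result, in the PD Set. Seroconversion at any time keeps Days 21 and 42.
- **That a positive stool marks higher titres.** No document says so, and shedding 28 days after the last dose may be rare or absent.
- **That a replacement would inherit a known allocation.** Section 10.6.6 does say "Replacement participants will be assigned the same randomisation as the participant they are replacing", but replacement after dosing is case by case, and nothing suggests replacing a fully dosed participant at Day 70.
- **That the Day 70 unblinding should be deleted.** Its value is debatable, since the stated action is the same for every positive culture. Deleting it would not fully restore the blind, because the site would still see the culture result and the antibiotic record.

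**Conclusion.** The inconsistency is real and sits in operative text: 10.6.9 cannot be followed together with 10.1 and 10.3. Two smaller conflicts accompany it: optional against definite unblinding, and disclosure to the Monitor against a bar on it.

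For each participant withdrawn under a literal reading, the loss is definite: the single serum sample after dose 3, the Day 84 safety assessments and clearance stool, and about the last 14 of the 84 days of the primary window. How many are affected rests on an assumed shedding rate, and any bias in the Day 84 GMT needs a further assumed titre difference. At low shedding the shift is small, and at zero the problem has no numerical effect. The case for correcting the text does not depend on those assumptions.

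**What to change.** Reconcile section 10.6.9 with sections 10.1 and 10.3 and the synopsis:

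1. In 10.6.9, state that disclosing allocation after a positive Day 70 stool culture is a planned step, not a code break that triggers withdrawal, and that these participants complete all Day 84 assessments and the Day 154 and 224 calls.
2. Use either *may* or *will* for this unblinding in both the synopsis and 10.3.
3. Give one rule on whether the Monitor learns the allocation, worded the same in the synopsis, 10.3 and 10.6.9.

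The rule for emergency and adverse-event-driven code breaks need not change for this purpose.

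The cost is a wording amendment, with no added visits, samples or participants. The small downside is that adverse events in these participants are graded open-label from about Day 70 to Day 84, which the plan already accepts by unblinding the Investigators.
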